**Liver function**

“ . . . p . . . (TBL) f Upper limit normal (ULN) and at least one of the following 2 conditions:

- Alanine aminotransferase (ALT) g ULN for at least one visit
- Aspartate aminotransferase (AST) g ULN for at least one visit.

DILI (drug-induced liver injury): At least one of the following 2 conditions:

- “ . . .
- ALT 5 ULN for at least one visit.

**Metabolic function**

Serious hypoglycemia adverse event

Treatment-emergent HbA1c: Shift from low/normal at baseline to high at least once.

**Renal function**

Treatment-emergent abnormal eGFR: Shifts

Mild at baseline to moderate/severe

Moderate at baseline to severe.

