| TEAE                    | Treatment-emergent adverse event: An untoward medical occurrence that emerges during a defined treatment period, having been absent pretreatment, or worsens relative to the pretreatment state, and does not necessarily have to have a causal relationship with this treatment.  |
| tmax         | time to maximum plasma concentration   |

**TRP** transient receptor potential

**TRPA1** transient receptor potential ankyrin 1

**WOCBP** women of childbearing potential

---

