### **6.12.4. Clinical Laboratory Evaluation**

The general analysis of laboratory parameters is described in the CPMP SAP Version 5.

In this ISA, laboratory results will be reported for the first 4-week, active-treatment period and separately for the entire 8-week study period.

Study NP02 will also consider the following analyses of lab analytes used to assess renal function. The planned summaries for these analytes are the same as those that have been described in the Study CPMP SAP Version 5; however, the reporting of these analytes will be separate from the general analysis of laboratory parameters.

Renal data analyses:

- Serum creatinine (change from baseline in mg/dL)
- Estimated glomerular filtration rate (eGFR; Chronic Kidney Disease Epidemiology Collaboration [CKD-EPI] algorithm using serum creatinine) Algorithm: Provided by central laboratory
- For eGFR calculation, we will summarize shift tables of eGFR changes for baseline vs. postbaseline by minimum, maximum and last observed eGFR result:
  - Category 1: Normal or increase in GFR ( 90 mL/min/1.73m^2)
  - Category 2: Mild reduction in GFR (60 to 89 mL/min/1.73m^2)
  - Category 3a: Moderate (a) reduction in GFR (45 to 59 mL/min/1.73m^2)
  - Category 3b: Moderate (b) reduction in GFR (30 to 44 mL/min/1.73m^2)
  - Category 4: Severe reduction in GFR (15 to 29 mL/min/1.73m^2)
  - Category 5: Kidney failure (GFR < 15 mL/min/1.73m^2 or dialysis).

Abnormal eGFR is specified below and will be summarized in the laboratory summary tables.

- Abnormal low: < 90 mL/min/1.73m^2
- Abnormal high: As specified by central laboratory.

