## 6.17. Totality of Evidence for Safety

The totality of evidence analysis approach for safety data has been briefly described in the CPMP SAP Version 5. This may be reported for any of the active treatment period, post-active treatment period, and entire 8-week study period. The key safety events to be considered for Study NP02 are listed below by domain:

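### The renal key safety event in SAP 6.17 cannot occur in a participant whose baseline eGFR is normal, however far it falls

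*SAP*

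**What the plan says.** SAP 6.17 sets out the totality-of-evidence approach for safety. It introduces its list with the words "The key safety events to be considered for Study NP02 are listed below by domain". Under renal function there is one event, treatment-emergent abnormal eGFR, defined by two shifts: "Mild at baseline to moderate/severe" and "Moderate at baseline to severe". The section makes the output optional: "This may be reported for any of the active treatment period, post-active treatment period, and entire 8-week study period".

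The eGFR categories are in SAP 6.12.4. Normal stands alone ("Category 1: Normal or increase in GFR"), and the next band down is separate ("Category 2: Mild reduction in GFR (60 to 89 mL/min/1.73m", with the unit continuing). Moderate is split into 3a (45 to 59) and 3b (30 to 44). Severe is Category 4 (15 to 29). Kidney failure is Category 5 (below 15, or dialysis). The same section plans shift tables of baseline against the minimum, maximum and last postbaseline eGFR, and treats any value below 90 as abnormal low.

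The metabolic domain, just above the renal one in 6.17, reads "Treatment-emergent HbA1c: Shift from low/normal at baseline to high at least once".

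**The concern.** Neither listed shift starts from normal. A participant with a normal baseline therefore contributes zero to the renal event by construction, in whichever arm. Large falls from normal are ignored, while a one-unit fall across the boundary between mild and moderate is counted, so the event does not rank declines sensibly.

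Two other places in the documents point towards including a normal baseline. The HbA1c event starts from low or normal. The treatment-emergent definition in Protocol 10.5 covers what was not there before treatment as well as what got worse ("having been absent pretreatment, or worsens relative to the pretreatment state"). That definition is written for adverse events, so it is context for the label used in 6.17 and not a binding rule for laboratory shifts.

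At stake is the renal line of the safety summary. A normal-to-severe fall would appear in the 6.12.4 shift table and add nothing to the key renal event, so two outputs of the same SAP would give different pictures. There is also a wording ambiguity: 6.17 does not say whether severe takes in Category 5.

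**Working it through.** The plan states no figure for this event, so there is none to reproduce. The check applies the 6.17 rule to the 6.12.4 bands.

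**Inputs**
- Bands in whole mL/min/1.73 m² (SAP 6.12.4): Category 1, 90 or more; 2, 60 to 89; 3a, 45 to 59; 3b, 30 to 44; 4, 15 to 29; 5, below 15. The comparison sign before 90 is lost in the text available. I read it as 90 or more, because Category 2 ends at 89 and abnormal low is below 90.
- Rule (SAP 6.17): mild to moderate or severe; moderate to severe.
- Eligibility (Protocol 5.2, criterion 3052): eGFR below 30 is excluded. No upper limit is visible, so participants with normal eGFR can enter. Other criteria are redacted or sit in the master protocol.
- Planned size (SAP 5.2): about 150.

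**Step 1: enumerate the worsening shifts.** Six ordered categories give 6 × 5 / 2 = 15 possible worsening shifts. The table shows how many count as written.

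| Baseline | Worsening shifts | Count, Category 5 separate | Count, Category 5 treated as severe |
|---|---|---|---|
| Normal | 5 | 0 | 0 |
| Mild | 4 | 3 | 4 |
| 3a | 3 | 1 | 2 |
| 3b | 2 | 1 | 2 |
| Severe | 1 | 0 | 0 |
| Total | 15 | 5 | 8 |

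The zero in the normal row does not depend on how Category 5 is read. With Category 5 kept separate, a fall from mild or moderate to kidney failure is not counted either.

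**Step 2: size of the falls.** The smallest uncounted fall from normal into each lower group is:
- to 3a: 90 − 59 = 31
- to 3b: 90 − 44 = 46
- to Category 4: 90 − 29 = 61
- to Category 5: 90 to below 15, more than 75

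The smallest counted fall is 60 − 59 = 1. Large falls from mild do count, for example 89 − 15 = 74.

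**Step 3: how many participants are affected.** The documents give neither the share with a normal baseline nor an event rate. Assuming a share of 10% to 50%: 0.10 × 150 = 15 and 0.50 × 150 = 75 participants who could not have the event. This counts people outside the definition. It says nothing about how many would have had a decline.

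**Step 4: the rule with a shift from normal to moderate or severe added.**
- Category 5 kept separate: 3 of 5 shifts from normal count, and 8 of 15 overall. Normal to kidney failure is still missed.
- Category 5 treated as severe: 4 of 5 from normal count, and 12 of 15 overall. The three left out are normal to mild, 3a to 3b, and severe to kidney failure.

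Both changes are therefore needed.

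**The case against.** The strongest case is that nothing is lost from reporting. SAP 6.12.4 commits to the shift tables, the abnormal-low summary and the change in creatinine, so every fall from normal is visible there, while 6.17 is optional. The general adverse event domain of 6.17 also counts related serious adverse events and discontinuations due to an adverse event, so a fall to kidney failure reported in one of those ways would enter the summary by another route. The HbA1c event is itself restricted by baseline, since anyone high at baseline cannot have it, so it does not prove an intention to cover all baselines. Finally, 6.17 does not cite the 6.12.4 bands, and the CPMP SAP Version 5, which briefly describes the approach, was not available.

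Much of this stands, and it limits the importance of the point. It does not rescue the definition:
- The adverse event route depends on how the fall is reported; a laboratory decline that is neither a related serious event nor a cause of discontinuation stays out.
- A deliberate restriction to larger or worse declines would not omit falls of 31 units or more that end in the same or worse categories as counted ones.
- The 6.12.4 bands are the only eGFR categories in either document, and they use the same words.
- The NP02 events are listed in 6.17 itself. A rule in the master SAP that changes them cannot be excluded. Nor can a line lost from the text, but the renal entry reads cleanly.
- 6.17 does not say which baseline applies to the post-active period. If it were reset at Visit 5, someone who had become mild by then could count, but a participant who is normal at the baseline in use still could not.

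**Conclusion.** The concern holds. Followed as written, the rule leaves out every decline from a normal baseline, so the count does not match what the event's label says. The change should be made, but the consequence is modest because the effect is confined to the optional 6.17 summary. How the event is weighted in that summary is left to the CPMP SAP Version 5.

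The structural result rests on reading the terms mild, moderate and severe in 6.17 as the 6.12.4 bands. The number of participants outside the definition rests on the assumed 10% to 50% share. Whether severe includes Category 5 is a separate ambiguity and does not alter the main conclusion.

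**What to change.** Before unblinding, reconcile the renal entry in SAP 6.17 with the bands in 6.12.4:

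1. Add a third shift, from normal at baseline to moderate or worse.
2. State that severe means Categories 4 and 5.
3. Refer to the 6.12.4 categories by number, and say that normal-to-mild and 3a-to-3b shifts are left to the 6.12.4 tables.

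The limits should be acknowledged. The shifts in item 3 are single-category steps but not always small: 120 to 60 is a fall of 60 units and would still not count. The event would also remain narrower than the abnormal-low rule of below 90. Severe to kidney failure would stay outside it too, although the eligibility floor of 30 at Visit 1 or Visit 2 should make a severe baseline uncommon.

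The cost is a few words of SAP text and minor table programming on data already collected. The only downside is that event counts may rise in either arm. I would expect the rise to be slight, but the documents give no event rate to confirm that. Made after unblinding, the same edit would be a post hoc change to a safety definition.

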## 6.18. Annual Report Analyses

Analyses will be produced as needed for the purposes of providing periodic safety reviews to regulatory agencies (for example, Development Safety Update Reports). Data from this ISA will be combined with data from other clinical studies that investigated LY3526318. In all analyses, a combined LY arm will be created which includes participants assigned to any dose of LY3526318 in the included studies, including LY-combination regimens.

The following data will be summarized by treatment group.

enrollment (ongoing and completed)

demographics (Race, ethnicity, and gender)

exposure

- cumulative number of subjects exposed to LY3526318
- cumulative number of subjects exposed to LY3526318 by age
- cumulative number of subjects exposed to LY3526318 by sex
- cumulative number of subjects exposed to LY3526318 by race

cumulative summary of serious AEs.

The following listings will be provided.

list of serious AEs during the reporting period

list of subjects who died

cumulative list of subjects who discontinued due to an AE (discontinued from treatment or study)

list of subjects who discontinued due to an AE during the reporting period.

Additional analyses may be added or omitted at the time of report submission as needed.

## 6.19. Clinical Trial Registry Analyses

Additional analyses will be performed for the purpose of fulfilling the Clinical Trial Registry (CTR) requirements.

Analyses provided for the CTR requirements include the following:

Summary of AEs, provided as a dataset that will be converted to an XML file. Both Serious AEs and Other AEs are summarized by treatment group and by MedDRA Preferred Term.

A serious AE is an AE that is considered Serious whether or not it is a treatment emergent.

An AE is considered in the Other category if it is both a TEAE and is not serious. For each Serious AE and Other AE, for each term and treatment group, the following are provided:

- the number of participants at risk of an event
- the number of participants who experienced each event term
- the number of events experienced.

Consistent with [www.ClinicalTrials.gov](http://www.ClinicalTrials.gov) requirements, Other AEs that occur in fewer than 5% of participants in every treatment group may not be included if a 5% threshold is chosen (5% is the minimum threshold).

AE reporting is consistent with other document disclosures for example, the Clinical Study Report (CSR) and manuscripts.

## 7. Unblinding Plan

The general unblinding plan is described in the CPMP SAP Version 5 and in the CPMP Blinding and Unblinding Plan Version 1. Unblinding considerations specific to Study NP02 are provided below.

### PKPD Analysis Planning

A limited number of prespecified individuals who are not part of the blinded study team and do not have direct site contact, data entry, or data validation responsibilities, may receive access to unblinded data, prior to an interim or final database lock, in order to initiate the PK and/or PKPD model development processes. This will be described in the unblinding plan. Information that may unblind the study during the analyses will not be reported to study sites or blinded study team until the study has been unblinded.

